6.2. Description of Study Procedures

Before any screening procedure is performed, informed consent will be obtained. Labs will be taken at baseline and months 3, 5, 7, 9, and 11 for the CAB-LA cohort and at baseline and months 3, 6, 9, and 12 for the Oral PrEP cohort (only collected through standard of care). Participants will complete a baseline evaluation and be introduced to a support group at baseline. Patients will complete assessments within the TheraPay App. Clinicians will complete assessments outside of the app. Patients in both cohorts will complete baseline demographic surveys in month 0, patient reported outcomes (PRO) data collection set 1 in months 1, 5, and 11 and PRO data collection set 2 in months 3, 9, and 12. Patients in the CAB-LA PrEP cohort will complete persistence assessments in months 1, 3, 5, 7, 9, and 11. Patients in the Oral PrEP cohort will complete persistence assessments every month from months 1 through 12. Clinic staff will complete surveys at baseline, month 6, month 12, and at the end of the study. The

schedule of assessments for the CAB-LA PrEP cohort, Oral PrEP cohort, and clinicians is presented in figure 6a. Instruments are in Appendix B for the CAB-LA cohort, in Appendix C for the Oral PrEP cohort, and Appendix D for clinicians. Patient incentives for completing the assessment activities are outlined in Appendix E.

6.2.1. Baseline Patient Demographic Survey

6.2.2. Medication Persistence

6.2.2.1. Definition: Continue to take medicines over time independent of adherence to the PrEP medication regimen.

6.2.3. Persistence Assessment CAB-LA

6.2.3.1. The proportion of participants who received at least one PrEP injection who remained on injectable PrEP or oral bridging at months 3 and 11 measured by the self-report assessment and validated with claims data.

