6.2.4. Persistence Assessment Oral PrEP

6.2.4.1. The proportion of participants who initiated oral PrEP who remained on oral PrEP at months 3 and 12 measured by the self-report assessment and validated with claims data period.

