6.2.6. Adherence Assessment CAB-LA

6.2.6.1. Adherence to the dosing schedule will be assessed at month 3 (early adherence) and end of study by:

A) Estimating the number of individuals who missed one or more consecutive injections without taking daily oral bridging PrEP while not on CAB-LA injections and mean and median number of injections missed during a 6- and a 12-month period.

6.2.7. B) Estimating the number of individuals who received the injections seven or more days later than their scheduled injection visit and the mean and median duration of delayed injections. Adherence Assessment Oral PrEP

6.2.7.1. Adherence to the dosing schedule will be assessed at months 3 (early adherence) and 12 by:

A) Estimating the number of individuals who reported three or more days of oral PrEP missed and the mean and median number of days they missed.

B) Estimating the number of individuals who had a gap of >90 days between the end of the days of supply of a dispensing and the start date of the next fill.

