6.14. STATISTICAL ANALYSIS

6.14.1. Study Endpoints

6.14.1.1. Medication Adherence and Persistence

Medication persistence is defined as continuing to take PrEP over time independent of adherence to the medication regimen. The proportion of

patients reporting receipt of CAB-LA or oral PrEP at months 3 (early) and end of study (late) will be measured through patient questionnaires and validation protocols. Medication adherence is defined as taking PrEP in line with medical advice.

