6.14.1.4. Implementation Outcomes for the Mobile App

Acceptability of the mobile app to support patients in taking PrEP will be measured by the Acceptability of Intervention Measure (AIM) at months 1, 5, and 11. Appropriateness of the mobile app to support patients in taking PrEP will be measured by the Intervention Appropriateness Measure (IAM) at months 3, 9, and 12.

6.14.1.5. Clinic Staff Acceptability, Appropriateness, and Feasibility of Providing Long-acting Cabotegravir Injections

Acceptability of the process for providing long-acting cabotegravir injections will be assessed by the Acceptability of Intervention Measure (AIM). Appropriateness of the process for providing long-acting cabotegravir injections will be assessed by the Intervention Appropriateness Measure (IAM). Feasibility of long-term use of cabotegravir injections will be assessed by the Feasibility of Intervention Measure (FIM). Willingness to sustain provision of long-acting cabotegravir injections and barriers to and facilitators for provision of long-acting cabotegravir injections will be assessed through a brief survey. The clinic staff surveys will be administered at baseline, month 6, month 12, and end of study.

7. Statistical Analyses

Baseline analyses will include tabulations of demographic and clinical variables of the study participants. Chi-square tests and t-tests will be used to compare these groups to determine if baseline differences exist. The distribution of each continuous variable will be inspected for outliers to determine whether a parametric or non-parametric approach should be applied. The Wilcoxon ranked sum test will be used for any variable that does not meet the statistical assumptions of the t-test. Variables found to be associated with persistence or adherence following univariate analysis will be included in multivariate models.

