To assess the co-primary endpoint of persistence at 3 months and end of study, the proportion of participants reporting continued receipt of injections in the CAB-LA cohort and the proportion of patients reporting continued use of PrEP by mouth in the oral PrEP cohort on the persistence assessment will be compared using chi square tests or Fisher's exact tests. Self-reported persistence will be validated by the medication possession ratio (MPR). MPR is defined as the number of days of medication dispensed during the study period divided by the number of days that the person should have received therapy. The percent of CAB-LA participants with MPRs ≥ 1.0 will be compared to the percent of oral PrEP participants with MPRs ≥ 1.0 using chi square tests or Fisher's exact tests. To assess the co-primary endpoint of adherence, chi square tests or Fisher's

exact tests will be used to compare the percent of CAB-LA participants who reported missing one or more injections during the study period to the percent of oral PrEP participants who reported three or more missed days of oral PrEP. The percent of CAB-LA participants who received any injections seven or more days later than their scheduled injection or oral PrEP participants who had a gap of >90 days between the end of the days of supply of a dispensing and the start date of the next fill will be compared.

Sample Size

Assuming adherence proportions of .90 and .65 and sample sizes of 70 and 35 in the CAB-LA and oral PrEP arms respectively, the 95% confidence interval for the difference between the CAB-LA proportion and the oral PrEP proportion is .0771 to .4229.

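### Late persistence is read a month later for oral PrEP than for CAB-LA, oral bridging is counted inconsistently, and a between-arm test of MPR ≥ 1.0 does not check self-report

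*Combined protocol and SAP*

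**What the plan says.** **Timing.** Section 6.2.3.1 counts CAB-LA participants who "remained on injectable PrEP or oral bridging at months 3 and 11". Section 6.2.4.1 takes oral participants "who remained on oral PrEP at months 3 and 12". Sections 6.14.1.1 and 7 and the Study Outcomes Table give only month 3 and end of study. That term is not defined, and for clinic staff it is listed apart from month 12: "The clinic staff surveys will be administered at baseline, month 6, month 12, and end of study" (6.14.1.5). Under 6.2, CAB-LA persistence surveys stop at month 11, but "Patients in the Oral PrEP cohort will complete persistence assessments every month from months 1 through 12". Section 7 compares the two proportions by chi-square or Fisher's exact test.

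**Bridging.** Section 6.2.3.1 counts oral bridging as persistent. The adherence rule in 6.2.6.1 also credits it, counting only injections missed "without taking daily oral bridging PrEP while not on CAB-LA injections". Section 7 instead uses "the proportion of participants reporting continued receipt of injections in the CAB-LA cohort", and for CAB-LA the outcomes table names injections and does not mention bridging. The first question of the CAB-LA persistence survey (Appendix B) asks about injections, but its two answers are that the participant is taking PrEP or has stopped taking it.

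**Validation.** Section 6.2.2.1 defines persistence as independent of adherence. Section 7 validates self-reported persistence by the medication possession ratio (MPR) and tests the percentage with MPR ≥ 1.0 between arms. Sections 6.2.3.1 and 6.2.4.1 name claims data for validation; the outcomes table names the EHR and a Medication Retention Ratio. No agreement analysis is described.

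**The concern.** These passages define a co-primary endpoint, and three parts of it are left open.

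- Oral participants have one more month in which to discontinue, and the test makes no allowance for exposure time. This favours the hypothesis in 2.3.1.
- A CAB-LA participant on oral bridging is persistent under 6.2.3.1 and not persistent under Section 7. The survey could record that person either way, so the 6.2.3.1 numerator cannot be built reliably from it.
- The validation asks whether possession was complete, which is a question about adherence. It asks this between arms, not between self-report and record in the same person.

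If these choices are settled after the data are seen, the late result can depend on who settles them.

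**Working it through.** **Inputs from the plan.** Arm sizes 70 and 35, and proportions .90 and .65, labelled adherence (Section 7, Sample Size). Injections at months 0, 1, 3, 5, 7, 9 and 11, and oral fills at months 0, 3, 6, 9 and 12 (6.13.1). Discontinuation means more than 3 consecutive months missed (6.6.1).

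**Assumed, because the plan gives no figure.** Constant discontinuation hazard; month-12 oral persistence of 80% to 40%; coverage of 30 days for the first injection and 60 for each later one; 90 days per oral fill; 30-day months unless stated.

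**The plan's own interval.** .25 ± 1.96 × √(.90×.10/70 + .65×.35/35) = .25 ± .1729, which is .0771 to .4229, as stated. The plan gives no corresponding figure for persistence.

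**1. Timing.** With month-12 persistence p, month-11 persistence is p^(11/12).

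| p at month 12 | at month 11 | gap (points) |
|---|---|---|
| .80 | .815 | 1.5 |
| .65 | .674 | 2.4 |
| .50 | .530 | 3.0 |
| .40 | .432 | 3.2 |

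If both arms had the same hazard, reading CAB-LA at month 11 and oral at month 12 would show these gaps in favour of CAB-LA.

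**2. Bridging.** Each participant moves CAB-LA by 1/70 = 1.4 points. Two recorded as stopped (2.9 points) outweigh the timing gap at .80 or .65; three (4.3 points) outweigh it at .50 or .40. The number who will bridge is unknown.

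**3a. MPR, CAB-LA.** All seven injections supply 30 + 6×60 = 390 days. Suppose one of the month 1 to 9 injections is missed without bridging and treatment then resumes:
- full credit over 12 months: 330/360 = 0.92
- credit capped at month 12: 300/360 = 0.83
- window closed at month 11: 270/330 = 0.82

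The gap is about 2 months, so 6.6.1 is not met, yet MPR is below 1.0 in each case. On-time use gives 390/360 = 1.08, 360/360 = 1.00 and 330/330 = 1.00.

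**3b. MPR, oral.** On-time use, by whether the month-12 fill counts:
- not counted: 360/365 = 0.99, or 360/360 = 1.00
- counted: 450/365 = 1.23, or 450/360 = 1.25

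If the month-12 fill counts, skipping one whole fill gives (450 − 90)/360 = 1.00, which passes on a 360-day window; on 365 days it gives 0.99. If the fill does not count, a fully on-time oral user fails on 365 days. The plan does not state the window, the days' supply or the handling of that fill.

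**3c. Agreement.** Suppose 60% are persistent by self-report and 60% by MPR (assumed, for arithmetic only). Participant-level agreement can then lie anywhere from 2×0.60 − 1 = 20% to 100%. Matching percentages do not show that the two sources agree.

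**The case against.** The month 11/12 split is not arbitrary. It follows each arm's last persistence survey and is repeated for retention in 6.14.1.2. For adherence, 6.2.6.1 and 6.2.7.1 pair end of study for CAB-LA with month 12 for oral, so end of study may simply mean each arm's last reading. The clinic-staff wording concerns other respondents. A gap of 1.5 to 3.2 points is small beside the half-width of 17.3 points in the plan's adherence interval. Month 11 also falls before the oral month-12 refill, so the oral record there rests on the month-9 fill and shows possession, not use. All of this stands, and it makes timing the minor part. It explains the split but does not justify it, since oral month-11 self-report is already collected.

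On bridging, exclusion 5.2.5 might seem to remove the problem, but it covers bridging before injections start, not afterwards.

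On MPR, a reader might infer that it can say nothing about persistence. That goes too far. With surplus supply uncounted and a full-period denominator, MPR ≥ 1.0 does imply continued supply; it is supportive but not necessary. Section 7 also does not exclude bridging supply from days dispensed, so a bridged gap could still reach 1.0. Nor is MPR the only validation source named. What remains is that several sources are named and none is compared with self-report participant by participant.

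**Conclusion.** The point holds on the current text, as something to put right before analysis. The timing mismatch is worth about 1.5 to 3.2 points in favour of CAB-LA under the constant-hazard assumption; month 3 is unaffected. The bridging conflict is worth 1.4 points per participant and can work against CAB-LA. MPR ≥ 1.0 misclassifies a participant who misses one unbridged injection and resumes (0.82 to 0.92), and under assumed 90-day fills it is not the same hurdle in the two arms.

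Three stronger readings are not supported:

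- **That the design manufactures a CAB-LA advantage.** The timing effect is small, bridging may offset it, and the net direction is unknown.
- **That bridging would overturn the result.** If .90 and .65 are borrowed as persistence rates, recording 5 of 70 as stopped gives 58/70 = .829 and an interval of -.002 to .360. But those rates are labelled adherence and the plan gives no bridging count.
- **That the MPR fault falls equally on both arms.** The fill and injection schedules make it unequal, in a direction that depends on conventions not yet stated.

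**What to change.** 1. **Timing.** Make month 11 the primary late comparison in both arms. Report oral month 12 against CAB-LA month 11 as a labelled sensitivity analysis.
2. **Bridging.** Reconcile 6.2.3.1, Section 7, the outcomes table and the first CAB-LA survey question to one persistence definition. Add a response that identifies bridging, and show the result both ways.
3. **Validation.** Report participant-level agreement (percent and kappa, by arm) between self-report and the records: claims, and WVHR dispensing and injection records. Set the record rule before analysis. Do not treat MPR below 1.0 as refuting persistence. Report MPR under adherence, stating days' supply, injection coverage, window, and the handling of bridging supply and the month-12 fill.
4. Carry the same wording into 6.2.4.1, 6.14.1.1, the outcomes table and Appendix G.

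**Cost.** Wording changes, one response option, a written record rule and a modest added analysis. No new visit or survey is needed: oral month-11 surveys are scheduled and 5.1.3 requires WVHR dispensing. The estimated difference may shift slightly in either direction, and the weakness of the oral month-11 record should be stated in the report.

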including access to free medications for uninsured patients. Additionally, WVHR utilizes a mobile health clinic to care for hard-to-reach populations. WVHR is in Kanawha County, which is designated by the CDC as one of the top vulnerable areas of rapid spread of HIV due to injection drug use. Due to its location, services provided, and focus on uninsured/underinsured individuals, the populations cared for by WVHR encompass those with high unmet needs and PrEP-related disparities, including women, persons who inject drugs (PWID), transgender persons, persons in rural areas, and persons with low-income. Importantly, WVHR is committed to sustaining the HIV prevention initiative after the proposed study has concluded, as stated in the letter from Chief Executive Officer, [name], DNP, APRN, BC, FNP

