5.1.3. PrEP dispensed by WVHR pharmacy

5.1.4. Access to a smart phone

5.2. Exclusion Criteria

5.2.1. <18 y/o

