13.1.5. Incentive Mapping

13.1.6. List of Tables

13.1.6.1. Study Procedures

13.1.7. List of Figures

13.1.7.1. Study Schema

13.1.7.2. Study Timelines

13.1.8. Forms for Safety Reporting

1. PROTOCOL SUMMARY

Title	A Transformative Approach Utilizing Behavioral Economics, Education, and Data Science to Support Patients Initiating PrEP with Retention-in-care and Medication Persistence
Funder	ViiV Healthcare
Study Design	Observational Cohort Study
Study Population	Patients >18 y/o who are newly started on PrEP at WVHR and have access to a smart phone with data.
Study Size	n = 105 (70 CAB-LA intervention participants and 35 oral PrEP participants)
Study Duration	12 months
Study Site(s)	West Virginia Health Right
Intervention Description	Participants will have been prescribed CAB-LA, daily FTC/TDF, or daily FTC/TAF in accordance with the WVHR standard of care by a licensed HCP prior to enrolling in the study. Those receiving CAB-LA will be in one arm and those receiving oral therapy will be in the other arm of the study.
Study Aim	To determine the persistence in injectable PrEP compared to Oral PrEP therapy
Primary Objectives	To evaluate medication persistence in patients receiving CAB-LA vs oral PrEP and who engage with a digital health companion program
Secondary Objective 1	Evaluate Retention-in-care in patients receiving CAB-LA vs oral PrEP
Secondary Objective 2	Evaluate PROs (including PrEP medication satisfaction, PrEP acceptance, stigma, and reasons for PrEP discontinuation) in patients receiving CAB-LA vs oral PrEP
Secondary Objective 3	Evaluate the acceptability, appropriateness, and helpfulness of a digital health companion program for PrEP

Secondary Objective 4	Evaluate the acceptability, barriers to, and facilitators for implementation of CAB-LA
--------------------------	--

Study Schema Figure

Figure showing study components and flow – organize by participant cohort (i.e. oral, LA, no PrEP)

Study Outcomes Table

Primary or Secondary Endpoint	Definitions	Type of Endpoint	Assessment Timepoint	Data Source	Intervention or Approach	Tool/Instrument for Endpoint
1. Primary Endpoint: PrEP adherence and Persistence	Proportion of patients reporting receipt of CAB-LA injections or use of oral PrEP at 3 months after PrEP initiation and end of study	Quantitative	M3 and end of study	Participant survey and EHR	Participant survey and EHR	Survey and Medication Retention Ratio

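### The record used to validate self-reported persistence is named inconsistently, and the only external one named, claims data, could miss free fills to uninsured participants and bias the between-arm MPR comparison

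*Combined protocol and SAP*

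**What the plan says.** The validation of self-reported persistence is described in six places.

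- **6.2.3.1 (CAB-LA):** persistence at months 3 and 11 is "measured by the self-report assessment and validated with claims data".
- **6.2.4.1 (oral PrEP):** persistence at months 3 and 12 is "measured by the self-report assessment and validated with claims data period".
- **6.14.1.1:** patient questionnaires plus validation protocols, which are not described.
- **Section 7, Statistical Analyses:** self-report is validated by an MPR. On the numerator, "MPR is defined as the number of days of medication dispensed during the study period"; the denominator is the days on which therapy should have been received. The percentage with an MPR of at least 1.0 is then compared between arms by chi-square or Fisher's exact test.
- **Study Outcomes Table:** the data source is "Participant survey and EHR", and the tool is a survey and a Medication Retention Ratio.
- **Appendix G:** a medication ratio.

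Three other places bear on the choice of source. Section 2.1 describes a clinic population that includes uninsured adults and an in-house pharmacy service "including access to free medications for uninsured patients". Inclusion criterion 5.1.3 requires "PrEP dispensed by WVHR pharmacy". The baseline survey in Appendices B and C asks about health coverage and offers uninsured as an answer.

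**The concern.** A claim is ordinarily a bill to a payer. A fill given free to someone with no payer would not be expected to produce one. The two endpoint definitions are the only text that names a validating record from outside the clinic, and that record is the one most likely to be incomplete for the population the study sets out to reach.

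Section 7 does not remove the difficulty. The MPR is a calculation and not a data source, and the section does not say where the dispensed days are to be read from. An analyst who built the MPR from claims would be following 6.2.3.1 and 6.2.4.1 to the letter. An uninsured participant supplied free throughout could then have a recorded MPR of zero despite unbroken use.

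What is at stake is the objective check on a self-reported co-primary endpoint. That check includes a formal between-arm test. Arms follow the baseline prescription chosen by shared decision (6.9 and 6.10), so nothing balances insurance coverage between them, and loss of fills from the record need not be equal.

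**Working it through.** **1. The plan's own figure.** Section 7 gives one computed result: a 95% interval of .0771 to .4229 for the difference between .90 (n = 70) and .65 (n = 35), stated for adherence.

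- SE = √(.90×.10/70 + .65×.35/35) = √(.001286 + .006500) = .0882
- Interval = .25 ± 1.96 × .0882 = .0771 to .4229

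This reproduces exactly. It does not depend on the validation source and is not in dispute.

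**2. What depends on the source.**

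| Analysis in Section 7 | Variable | Affected by missing claims? |
|---|---|---|
| Co-primary persistence test | Self-report on the persistence assessment | No |
| Validation test | Percentage with MPR of at least 1.0 | Yes, if claims supply the dispensed days |

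No passage reclassifies a participant whose self-report is not confirmed, and no passage says how disagreement between self-report and the validator is handled.

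**3. How the bias would arise.** Let *m* be an arm's true share with MPR of at least 1.0, and *u* the share of those people whose fills leave no claim. If a missing claim counts as nothing dispensed:

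- observed share = *m*(1 − *u*)
- error in the difference (CAB-LA minus oral) = *m*(oral)·*u*(oral) − *m*(CAB)·*u*(CAB)

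The error can take either sign. With equal *m* in the two arms it is zero when *u* is equal.

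**4. Illustration.** The documents give neither *m* nor *u*, so every value of *u* below is an assumption.

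With *m* = .80 assumed in both arms, so that the true difference is 0:

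| *u* CAB-LA | *u* oral | Observed CAB-LA | Observed oral | Difference |
|---|---|---|---|---|
| 20% | 20% | .80×.80 = .64 | .80×.80 = .64 | 0 |
| 10% | 30% | .80×.90 = .72 | .80×.70 = .56 | +.16 |
| 30% | 10% | .80×.70 = .56 | .80×.90 = .72 | −.16 |

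With the plan's .90 and .65 borrowed for *m*, although they are stated for adherence, and the interval formula of step 1:

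| *u* CAB-LA | *u* oral | Difference | 95% interval |
|---|---|---|---|
| 0 | 0 | .250 | .077 to .423 |
| 10% | 10% | .225 | .038 to .412 |
| 20% | 20% | .200 | .004 to .396 |
| 30% | 30% | .175 | −.025 to .375 |
| 10% | 30% | .355 | .166 to .544 |
| 30% | 10% | .045 | −.154 to .244 |

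Equal loss shrinks a real difference. Unequal loss can inflate it or nearly remove it.

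**5. With clinic records as the source.** Criterion 5.1.3 requires dispensing by the clinic's pharmacy, and there is one site. A free fill should therefore appear in the dispensing record as a billed one does. Loss from missing claims is then *u* = 0, and the illustrated difference stays at .250.

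**The case against.** The strongest reply is that the plan already points to the right record. Section 7 counts days dispensed rather than days billed, the outcomes table lists the EHR, and all study PrEP must come from the clinic's own pharmacy. On that reading, claims data is loose wording in two definitions, possibly meaning the pharmacy's own fill records, since the term is never defined. No passage states that a free fill leaves no claim, or that study PrEP is among the free medicines.

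Much of this stands. The absence of a claim is an inference, and a careful analyst might well use dispensing records unprompted. But the same two definitions govern the persistence endpoint, Section 7 names no source that would override them, and there is no rule for a participant without claims. The ambiguity remains.

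A reader might go further and infer that persistent uninsured participants would fail validation and be counted as non-persistent in the primary result. The documents do not support that: the co-primary test is on self-report, and failing validation has no defined consequence.

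A reader might also attach an error rate to the problem. With a true 80% in both arms and 10% versus 30% uninsured, an uncorrected chi-square test at 70 and 35 would reject about 38% of the time, and Fisher's exact test about 33%. Those figures rest on an assumed 20-point imbalance and an assumed 80%. The plan tests the percentage with MPR of at least 1.0, for which it gives no expected value; it does not test a persistence rate reduced by the uninsured share. Reversing the imbalance moves the bias towards the other arm, and with equal shares rejection stays at about 5% or below.

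**Conclusion.** The point holds as an unresolved inconsistency with a plausible route to bias in the validation analysis. The validating record is described in several incompatible ways, and the only external record named may leave out unbilled fills. If claims supply the MPR, uninsured participants who are still on PrEP could be scored as not possessing medication, and the between-arm MPR comparison could be biased in either direction.

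This rests on two inferences: that claims data means payer claims, and that free fills of study PrEP produce none. It also requires that some enrolled participants are uninsured; for the comparison to show a false gap between equally persistent arms, coverage must differ by arm. The documents do not give the uninsured share, so the size cannot be estimated, and the tables above show only direction and sensitivity.

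The self-report persistence test and the plan's stated confidence interval are not affected. The matter should be corrected because the fix is simple and the validation is the only objective support for a self-reported endpoint.

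**What to change.** - **6.2.3.1, 6.2.4.1 and Section 7:** replace claims data with clinic records as the single source for both validation and the MPR. Use the clinic pharmacy's dispensing records for oral PrEP, including oral bridging in the CAB-LA arm, and EHR injection-administration records for CAB-LA. State how injection records are converted to days for the MPR.
- **6.14.1.1, the Study Outcomes Table and Appendix G:** use the same source and the single name MPR.
- **Section 7:** state how disagreement between self-report and the record, and missing validation data, are handled. Report validation completeness by arm and by baseline coverage.

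The cost is a wording amendment. The records are held at the one study site and should cover every eligible participant, baseline coverage is already collected, and no request to payers is needed.
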